This investigation aims to assess the clinical performance and cost-effectiveness of Biatain® Silicone compared to current standard of care (filler, that functions as a primary dressing to manage exudate and the gap/space between the wound bed and the dressing, covered by a secondary dressing on top) defined in this study as Mepilex® Border and AQUACEL® Extra Hydrofiber Dressing, in the treatment of chronic wounds - venous leg ulcers and diabetic foot ulcers with wound depth down to 20 mm.

3. Objectives of the clinical investigation

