8.	For subjects with diabetes, has HbA1c ≤ 10% or ≤ 86 mmol/mol, measured within the last 3 months prior to inclusion	To mitigate the risk of reduced healing due to poorly managed diabetes

Table 1: Specifications related to Inclusion criteria 5

Wound diameter (cm)	Maximum wound depth (mm)			
6.0-10	20			
5.5-5.9	11			
5.0-5.4	10			
4.5-4.9	9			
4.0-4.4	8			
3.5-3.9	7			
3.0-3.4	6			
2.5.2.9	5			
2.0-2.4	4			
1.5-1.9	3			
1.0-1.4	2			

¹ depth at the deepest point in the wound bed ² diameter measured at the widest point of the wound

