6.1.2. Exclusion criteria

Table 3: Exclusion criteria

clus	sion criteria	Justification
1.	Wound is infected. For DFUs, has infection severity mild-severe according to the IWGDF/IDSA guideline (Appendix 5). For VLUs, has 2 or more clinical signs of infection as defined in protocol, based on clinical judgement by investigator/tissue viability nurse (Appendix 6)	Anti-microbial dressings are usually used for infected wounds in this study setting, according to recommendation. For identification of infection in DFUs, the validated IWGDF/IDSA system will be used. No similar validated scoring system currently exist for VLUs. For this reason, clinical signs are used as an indicator of infection according to clinical practice; The presence of 2 or more clinical signs of infection, will exclude subjects with VLUs from participating in the study.
2.	Wounds is with exposed tendons, is with bones or has fistulas	Complicated wounds which may require different treatments and have different healing patterns
3.	Wound is with cavity, or is undermined or tunnelling	Due to potential depth of wounds
4.	Subject is receiving chemotherapy	The skin undergoes major changes because o radio- and/or chemotherapy, and therefore it can be more fragile during wound management.
5.	Subject has ankle-brachial pressure index (ABPI) below 0.8 (measured at a frequency according to local standards)	Compression therapy is contraindicated in subjects with low ABPI
6.	Wound is larger than 10 x10 cm	Larger wounds are likely to have a higher %- area reduction which may cause bias in the overall sample size.
7.	Currently enrolled in another wound care device investigation unless co-enrolment has been agreed with the sponsor	To avoid bias

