Analysis of the primary endpoint:

The percent wound area reduction (WAR) will be analyzed by an analysis of variance with treatment and wound type (VLU and DFU) as fixed effects and wound area at baseline as covariate.

The mean WAR for each treatment group will be estimated together with the 95% confidence interval. Further, the difference in mean including a 95% confidence interval between the 2 treatments will be estimated.

Analysis of the secondary endpoint:

The secondary endpoint, total cost, will be calculated as the number of products used during the investigational period multiplied by the unit price of the product. Unit price will be extracted from Drug Tarif on the date of Last Patient Out.

This secondary endpoint will be analyzed by comparing the mean cost in the two groups assuming the cost data to be normally distributed. It will be tested on a 2-sided 5% test level if the difference in mean between the two treatments is zero. Further, the mean cost for each treatment will be estimated together with a 95% confidence interval.

Analysis of exploratory endpoints:

Percentage wound depth reduction will be analyzed by the same model as described for the primary endpoint but with wound depth at baseline as covariate.

Similarly, the two endpoints related to EQ-5D-5L (the index score and the VAS score) will be analyzed by an analysis of variance with treatment as a fixed effect and the baseline measure as covariate.

The two endpoints; responder defined as a subject reaching ≥ 30% wound area reduction within the 4-week investigation period (Yes/No) and wound healed during the investigation period (Yes/No) will be analyzed by a logistic regression model with treatment and wound type (VLU or DFU) as fixed effects and wound area at baseline as covariate.

Analysis of safety endpoints:

Adverse events will be listed and summarized, if relevant. Device deficiencies and concomitant medication will be listed.

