10.2. Sample size

The primary endpoint is the percent WAR from baseline to week 4. The sample size calculation assumes that the standard deviation of WAR in each group will be similar to what was estimated in the Biatain-Ag meta-analysis, namely SD=43%(13).

A sample size of 40 completing subjects in each arm will result in a study that is powered by 80% to get a width of a 95% confidence interval for the difference in mean WAR between the two treatments of less than +/-21%. This is based on an analysis of assumed normally distributed data.

Further, the width of the 95% confidence interval for the estimated mean WAR in each treatment group will with high probability (power of 89%) be less than +/- 15%.

The expected width of the confidence intervals based on a total of 80 subjects is deemed adequate to be able to compare the performance of the 2 treatments.

To account for lost to follow-up/dropout rate of 20%, 100 subjects are required for this study.

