10.3. Level of significance and power

A two-sided significance level of 5% will be applied. For information regarding the power see section 10.2.

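### Baseline wound depth is absent from the primary model and no planned analysis relates the wound area result to depth, although the objective covers filler replacement in wounds as deep as 20 mm

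*Combined protocol and SAP*

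**What the plan says.** Section 2 sets the aim as comparing one foam with filler plus secondary dressing "in the treatment of chronic wounds - venous leg ulcers and diabetic foot ulcers with wound depth down to 20 mm", and explains the product's expected benefit by its filling the space above the wound bed.

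Depth at entry (section 6.1.1):
- Inclusion 4 caps depth at 20 mm.
- Inclusion 5 and Table 1 cap depth by diameter, from 2 mm (1.0–1.4 cm) to 11 mm (5.5–5.9 cm) and 20 mm (6.0–10 cm). No minimum depth is set.
- Inclusion 6 requires that the wound exude enough to need a filler under a secondary dressing. The stated reason is to enrol wounds that would ordinarily receive the comparator regime.

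Section 6.1.2, exclusion 3, removes wounds under the wording "Wound is with cavity, or is undermined or tunnelling". The reason given is potential depth, and cavity is not defined.

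Depth is recorded at V1 and at each later scheduled visit while the wound is unhealed (sections 5.6 and 7.2). Randomisation is stratified by wound type only (section 5.8). The primary WAR model is an analysis of variance "with treatment and wound type (VLU and DFU) as fixed effects and wound area at baseline as covariate". Baseline depth is a covariate only for the exploratory depth-reduction endpoint. Section 10.1 leaves room for further exploratory work on subsets but does not name depth. Section 10.4 asks that the arms be comparable on wound area, without a numerical margin, and that mean cost be significantly lower with the test product.

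**The concern.** The plan itself treats depth relative to diameter as deciding whether the foam can conform: inclusion 5 is built on it. Yet nothing in section 10 asks whether the WAR difference changes with depth. If most enrolled wounds are shallow, the pooled estimate mostly describes wounds with little space to fill. Should the foam do worse in deeper wounds, that could go unseen while the conclusion is worded for the whole range up to 20 mm. Because success means finding the arms comparable, a pooled difference pulled towards zero would favour success.

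A second, smaller matter is that a baseline measurement that may be prognostic is collected and then left out of the primary model.

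**Working it through.** **Inputs.** From section 10.2: SD of WAR 43 points and "A sample size of 40 completing subjects in each arm", so 80 in total. From section 10.3: two-sided 5%. Assumed, because the documents do not give them: the share of deeper wounds, any true difference in them, and the residual variance explained by depth.

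**1. The plan's own precision figure.** Section 10.2 calls the study "powered by 80% to get a width of a 95% confidence interval for the difference in mean WAR" within ±21 points. The probability that the half-width stays below h is P(χ²_df ≤ df × (h / (t × SD × k))²).
- Difference: k = √(2/40) = 0.2236, df = 78, t × SD × k = 19.14. With h = 21 the probability is 89.4%; the plan states 80%.
- Single arm: k = 1/√40, df = 39, h = 15. The probability is 80.6%; the plan states 89%.

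The two stated probabilities look exchanged. That is a separate matter and does not harm the sample size: 80/(1 − 0.20) = 100. The benchmark used below is the half-width of about ±19.1 points for the difference.

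**2. What Table 1 allows.** Below 3 cm diameter the depth caps run from 2 to 5 mm. Only wounds of 6 cm or more may exceed 11 mm. Up to 5.9 cm, each cap divided by the lower edge of its diameter band is 0.2 (for example 4 mm / 20 mm). A 4 mm depth is therefore at the limit in a 2 cm wound, but has a ratio of only 4/80 = 0.05 in an 8 cm wound.

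**3. Precision in deeper wounds.** Half-width = t(0.975, 2n − 2) × 43 × √(2/n).

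| Assumed share deeper | n per arm | 95% CI half-width (points) |
|---|---|---|
| 100% | 40 | 19.1 |
| 50% | 20 | 27.5 |
| 25% | 10 | 40.4 |
| 20% | 8 | 46.1 |
| 10% | 4 | 74.4 |

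For the contrast between deeper and shallower wounds, half-width = t(0.975, 76) × 43 × √(2/(40q) + 2/(40(1 − q))), where q is the share deeper. This gives 38.3 at q = 50% and 44.2 at q = 25%.

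**4. Dilution, as illustration only.** Suppose a true difference of 30 points in deeper wounds and none in shallow wounds. The pooled difference is 30q. The chance that the 95% CI excludes zero in that direction (normal approximation, SE = 43 × √(2/40) = 9.6) is as follows.

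| q | Pooled difference (points) | Chance CI excludes zero |
|---|---|---|
| 100% | 30 | 88% |
| 75% | 22.5 | 65% |
| 50% | 15 | 34% |
| 25% | 7.5 | 12% |

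A depth main effect in the model would leave these pooled differences unchanged, since they average over the same mix of depths.

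**5. What the covariate would gain.** Narrowing = 1 − √(1 − R²); equivalent completers = 80/(1 − R²).
- R² = 0.05: 2.5%, equivalent to 84 completers.
- R² = 0.10: 5.1%, equivalent to 89.
- R² = 0.15: 7.8%, equivalent to 94.

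Table 1 ties maximum depth to diameter, and baseline area is already in the model, so the added R² may lie below this range.

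**The case against.** The strongest reply is inclusion 6: only wounds judged to need a filler enter, so every subject is relevant to replacing it. Section 2 also gives the filler two roles, managing exudate and managing the space, so a shallow, heavily exuding wound still tests part of the question. This stands, and it rules out two readings that a reader might infer: that the trial admits wounds with no need for a filler, and that the regimes must perform alike in shallow wounds. The documents support neither. It does not remove the concern, because the criterion rests on exudate and leaves deeper wounds unexamined.

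The plan also covers part of the ground. Baseline summaries include minimum and maximum, so the enrolled depth range will be visible. Depth reduction is modelled by treatment, conformability is rated at V3 and V5, and subset analyses are permitted. None of these relates the WAR difference to baseline depth; conformability has no model, and the subsets are unspecified.

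A reader might also see a contradiction between exclusion 3 and inclusion 4. This is not established: cavity stands beside undermining and tunnelling and can be read as concealed depth, which is compatible with open wounds up to 20 mm. What stands is that the term is undefined.

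Finally, depth-specific estimates will be imprecise, in a study that calls itself exploratory. That is true, and it is why they should be descriptive.

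**Conclusion.** The concern holds in a limited form. The plan measures depth, frames its objective by depth, and then has no analysis that would show whether the primary result depends on it. A comparable result could rest mainly on shallow wounds. The extent cannot be determined, because the depth distribution is unknown; the shares, the 30-point difference and the R² values above are assumptions.

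A reader might infer that leaving depth out of the model biases the comparison or pushes it towards no difference. It does not: randomisation protects the comparison, and the omission costs only precision, 2.5% to 8% of the interval width under an assumed R² of 5% to 15%, possibly less. The expected ±19.1 is already inside the planned ±21. The main gap is the missing depth-specific estimate and a conclusion not limited to the depths studied.

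**What to change.** Before database lock, amend section 10.1 as follows.

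1. Add baseline depth (mm) as a covariate in the primary WAR model.
2. Pre-specify, as a descriptive analysis, the treatment difference in WAR with 95% confidence intervals by baseline depth, or by depth relative to diameter, which is the construct behind inclusion 5. Fix the bands or the form of the interaction in advance. Report baseline depth by arm and limit the conclusion to the depth range actually enrolled.

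Both use data already collected and need only analysis wording. The downside is wide intervals (about ±46 points at an assumed 8 per arm), which can neither establish nor refute comparability in deeper wounds, and a claim that may be narrower than 20 mm.

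Separately, the sponsor should reconcile the meaning of cavity in exclusion 3 with inclusion 4. This review does not choose the rule. Section 12 lists a change to inclusion criteria as an example of a significant change requiring ethics committee notification, so an eligibility change here could carry that cost too.

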5.6. Demography and potential compromising factors

The following baseline data will be collected and reported at the Baseline Visit (V1) by the Principal Investigator or delegate:

- Age (years) at time of inclusion
- Height (cm)
- Weight (kg)
- Gender (male/female)
- Smoking (yes/no)
- Alcohol (units per week)
- Comorbidities affecting wound healing (diabetes, venous insufficiency, peripheral arterial disease, cardiopulmonary conditions, immune deficiencies, dementia or other as assessed relevant by investigator)
- Concomitant medication
- Wound type (VLU or DFU)
- Duration of wound (date of onset)
- Wound dressing at time of inclusion
- Wound size (measured by photo uploaded in a digital photo-planimetry software system)

Wound depth (mm)

To ensure optimal conditions for wound healing for VLUs, compression therapy must be performed, according to standard of care, such as compression therapy-bandage, compression sock, or other.

To ensure optimal conditions for wound healing for DFUs, off-loading must be performed according to standard of care based on subject need (wound location), preference and resources available. Methods of off-loading must be documented. Common methods to off-load the foot include bed rest, wheelchair, crutch-assisted gait, total contact casts, felted foam, half shoes, therapeutic shoes, and removable cast walkers.

Subjects who may require another dressing than the investigational test product(s) (e.g., an antimicrobial dressing superabsorbent dressing or other) will be followed during the four weeks follow-period. If other relevant wound care products are required to be used in addition to the test products, as part of standard of care (e.g., barrier cream), this must be recorded.

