5.8. Randomization Procedure

All included subjects that meet the inclusion and exclusion criteria will be randomized to one of two treatment groups. Randomization will be centralized using Medidata RAVE and stratified based on wound type (VLU or DFU).

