6.1.1. Inclusion criteria

Table 2: Inclusion criteria

clus	ion criteria	Justification			
1.	Has given written consent to participate by signing the Informed Consent Signature Form	To meet Helsinki declaration			
2.	Is at least 18 years of age and has full legal capacity	To meet Helsinki declaration			
3.	Has a venous leg ulcer (VLU) (C6 of the CEAP classification(1)) or a non-infected diabetic foot ulcer (DFU) with a duration longer than 8 weeks but no longer than 24 months (Appendix 4)	VLUs and DFUs are some of the most prevalent chronic wounds, they are both categorized as hard to heal ulcers and are most likely to require filler and secondary dressing due to exudate levels and dimensions of the wounds. To ensure reasonable recruitment time, both wound types will therefore be included in the study, and stratification will be made to ensure equal distribution of both wound types in the two arms			
4.	Has a wound with depth ¹ down to 20 mm	To comply with product specification of Biatain ® Silicone in terms of conformability			
5.	Has a maximum wound depth ¹ relative to wound diameter ² with specifications presented in table 1	To quantify conformability, it is essential to ensure that the dressing can conform relative to the width of the wound, which means how the foam increases in height (the swelling rise), when exposed to wound fluids, relative to the diameter of the wound. In Coloplast, the definition of a wound bed conforming dressing is defined as a dressing that conforms to an Alpha (α) value of 0.2, which is also the lower specification limit for Biatain® Silicone (18). However swelling rise has demonstrated to reach maximum of ~ 2 cm in tests with fence sizes (simulated wound diameter) ≥ 6 cm (19). Thus, wound-α is therefore not relevant for these wounds in this study due to inclusion criteria #4.			
6.	Has a wound with exudate levels requiring a filler and a standard secondary dressing	To include wounds that would normally require the comparator dressing regime and ensure that the treatment is aligned with the indications of the dressings			

7.	Has acceptance of compression therapy in case of a VLU or off-loading in case of a DFU, according to local standards	To ensure optimal conditions for wound healing, compression therapy must be performed for VLUs, according to standard of care. For DFUs, off-loading must be performed according to standard of care based on subject need (wound location), preference and resources available

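### Prespecify log wound duration as a covariate in the linear wound-area and wound-depth models: an optional, low-cost gain in a plan that is valid without it

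*Combined protocol and SAP*

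**What the plan says.** Section 10.1 fits an analysis of variance to the primary endpoint, with treatment and wound type "as fixed effects and wound area at baseline as covariate". Percentage wound depth reduction uses the same model with baseline depth in place of baseline area. The responder and healing endpoints use logistic regression with treatment, wound type and baseline area. Wound duration is in none of these models, and no duration-adjusted sensitivity analysis is named.

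Duration is nevertheless available. Section 5.6, headed "Demography and potential compromising factors", lists "Duration of wound (date of onset" among the items collected at V1, and section 7.2 repeats it. Section 6.1.1 admits ulcers "with a duration longer than 8 weeks but no longer than 24 months". Under section 5.8, randomisation is "stratified based on wound type (VLU or DFU" only. Baseline variables are summarised descriptively (section 10.1), so an imbalance in duration would be visible but would not enter the estimate.

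Section 10.2 sets the sample size by the width of the confidence interval for the difference in mean WAR, using an SD of 43 and taking no credit for covariates.

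**The concern.** Taking 24 months as about 104 weeks, eligible durations span a 13-fold range (104/8 = 13). If older ulcers shrink less over four weeks, part of the residual spread in WAR could be explained by a variable already in the database. In addition, with about 40 completers per arm, a chance difference in duration between the arms would move the estimated treatment difference.

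Three features make this worth a line in the plan.

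- No comparability margin is given. The sample size rests on interval width, and section 10.4 asks only that the arms be comparable on wound area, alongside a significantly lower mean cost. Readers will judge both the location and the width of the WAR interval.
- The analyses are also run on a per-protocol set that drops subjects for events after randomisation, such as infection, another dressing or a change of therapy. Randomisation does not guarantee balance on duration in that set.
- The trial is open-label. A covariate added after an imbalance has been seen would be open to challenge as post hoc.

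**Working it through.** **Inputs.** SD 43 points, 40 completers per arm, target half-width 21 for the difference and 15 per arm (section 10.2); two-sided 5% (section 10.3); model terms (section 10.1). The partial correlation r between duration and WAR, given wound type and baseline area, is not in the documents. It is an assumption, shown from 0 to 0.4.

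**The plan's own figures first.** Half-width = t(0.975, df) × s × √k, where the sample SD s gives s²·df/43² a chi-square distribution.

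- Difference, df 78, k = 2/40: expected half-width 1.991 × 43 × √0.05 = 19.14. P(half-width < 21) = 0.894, against 80% stated.
- One arm, df 39, k = 1/40: P(half-width < 15) = 0.806, against 89% stated.
- Enrolment: 80/(1 − 0.20) = 100, as stated.

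The two stated probabilities match the results almost exactly if exchanged, so they look transposed in section 10.2. That is a separate matter. Here it means only that precision for the difference is better than stated.

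**Planned model without duration.** The residual df are 80 − 4 = 76. Half-width = 1.992 × 43 × √0.05 = 19.15, and P(< 21) = 0.890. This treats 43 as the residual SD after wound type and baseline area. If those terms explain some variance, every half-width and shift below shrinks in proportion and the percentage changes stay the same.

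**With log duration added.** The residual df are 75, the residual SD is 43 × √(1 − r²), and the variance carries an approximate extra factor 1 + 1/75 for estimating one more slope:

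half-width = t(0.975, 75) × 43 × √(1 − r²) × √(0.05 × (1 + 1/75)) = 19.28 × √(1 − r²)

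A one-standard-error imbalance in duration shifts the unadjusted difference by r × 43 × √(2/40) = r × 9.615.

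| r (assumed) | half-width | change from 19.15 | P(< 21) | shift removed (points) |
|---|---|---|---|---|
| 0 | 19.28 | +0.7% | 0.871 | 0 |
| 0.1 | 19.18 | +0.2% | 0.884 | 1.0 |
| 0.2 | 18.89 | −1.3% | 0.919 | 1.9 |
| 0.3 | 18.39 | −4.0% | 0.960 | 2.9 |
| 0.4 | 17.67 | −7.7% | 0.989 | 3.8 |

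Break-even: √(1 − r²) = 19.15/19.28, so r is about 0.12.

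**Check by simulation.** Each value of r from 0 to 0.5 was run 20,000 times, with normal data, 40 per arm and no other covariates. With duration omitted, the mean estimated difference was within 0.1 point of the true zero and coverage of the 95% interval was 0.949 to 0.952. With duration included, coverage was 0.950 to 0.952, and mean half-widths were 19.21, 18.84, 18.34 and 17.60 at r = 0, 0.2, 0.3 and 0.4, close to the formula.

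**The case against.** The strongest reply is that nothing here is an error. The model already holds the stratification factor and baseline area, the two variables that the plan itself ties to healing: section 5.1 for wound type, and the justification of exclusion criterion 6 for size. Section 5.6 lists duration beside about a dozen other items and does not single it out as prognostic. A wide eligible range shows spread, not association. The trial calls itself exploratory, the planned precision uses the unadjusted SD, and at r of 0.2 to 0.3 the gain is only 1.3% to 4.0% of the half-width.

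All of that stands, and it rules out several stronger readings that a reader might infer.

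- *That the plan is losing precision.* This depends on a correlation the documents do not give. Below about 0.12, adding duration widens the interval slightly.
- *That the primary comparison is biased or its interval invalid.* Randomisation balances duration in expectation, and the unadjusted interval already allows for chance imbalance, as the coverage figures show.
- *That adjustment is free.* It costs one degree of freedom and up to about 0.7% in width.
- *That the same gain carries over to the responder and healing models.* The arithmetic is for a linear model. In logistic regression an added covariate changes the odds ratio being estimated and need not narrow its interval.

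The objection does not dispose of the per-protocol set, the analysis by product actually received (section 6.5) or the 20% dropout allowance. In those settings the argument from randomisation is incomplete, and adjustment is a partial safeguard. The documents do not show that duration predicts exclusion or dropout, so this is a reason for prudence and not evidence of bias.

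**Conclusion.** This is an optional improvement to a valid plan. Wound duration is collected, wide-ranging, unstratified and unadjusted. Prespecifying it would leave the half-width between about 0.7% wider (r = 0) and 7.7% narrower (r = 0.4), and would remove a shift of about 1.9 to 2.9 points per standard error of imbalance at r of 0.2 to 0.3. The case rests on the asymmetry between a very small worst-case cost and a larger possible gain, and on fixing the covariate before anyone can see an imbalance.

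The figures assume SD 43 as the residual SD, 40 completers per arm, roughly normal data, a linear effect of log duration and an r that the documents do not supply. They do not support saying that the planned analysis is wrong or that the stated precision is at risk.

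**What to change.** In section 10.1, add log(wound duration at baseline) as a covariate in the WAR model and the wound-depth model, beside the terms already there, for both the ITT and PP analyses. The log is suggested because the range is wide. Define duration as the V1 date minus the date of onset, and state how an incomplete onset date is handled. Leave the logistic models unchanged. Record the change before database lock and before the statistician is unblinded. If the sponsor prefers to keep the primary model, name the duration-adjusted model as a sensitivity analysis instead.

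Cost: one model term, one degree of freedom and no new data. If duration proves not to be prognostic, the interval is about 0.1 point wider on each side (19.28 − 19.15 = 0.13). The sample size does not change.

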Withdrawn subjects must also complete the Termination visit, regardless of the reason for withdrawal. Extra visits for additional wound assessments and dressing changes due to a clinical need will be registered as unscheduled visits. See section 7.2 for clinical investigation related procedures and assessments.

If the wound condition changes during the investigation and requires another treatment, based on a clinical evaluation, the PI or delegate must change the dressing regime and document the alternative treatment or therapy. The subject must continue in the investigation and all procedures must be performed, if possible.

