10.1. Statistical design, method, and analytical procedures

The primary objective will be evaluated by analyzing the primary endpoint whereas the analyses of the exploratory endpoints will be used to further evaluate and explore the primary objective. The secondary objective will be evaluated by analyzing the secondary endpoint.

All baseline measurements, endpoints and assessments will be summarized by descriptive statistics and/or listed. Descriptive statistics for continuous variables are presented with N, Mean, SD (standard deviation), Median, Min and Max, where N denotes the number of subjects contributing with non-missing data. For discrete variables, descriptive statistics are presented with N and percentage, where percentage is based on the total number of subjects/observations with non-missing data.

As it is an exploratory study no adjustment for multiple testing will be applied.

All statistical analysis will be performed with SAS (version 9.4/Enterprise Guide version 7.1)

Definition of analysis populations:

The Intention to Treat (ITT), Safety and Per Protocol (PP) populations will be defined at a formal data review meeting before data base lock. As a minimum, the data manager, the clinical manager, the scientific manager, and the statistician will be involved in the classification of subjects according to the below described criteria.

The ITT population (full analysis set) will be constituted by all randomized subjects with valid informed consent who have been exposed to at least one product.

The PP population will constitute a subset of ITT subjects who:

· fulfill the inclusion/exclusion criteria

- have not used other dressings than the investigational test product(s) during the study period
- Have not had a wound infection during the study period
- have not shifted therapy during the study period

Any exclusion of subjects from the ITT/PP populations must be documented.

Invalid individual datapoints may be omitted from the analysis even though the corresponding subject is part of the ITT/PP populations. Any exclusion of data points will be documented

The Safety Population will constitute by subjects who have given informed consent.

All statistical analysis will be based upon the ITT and PP populations, whereas adverse events and device deficiencies will be assessed based on the Safety population.

Considering the data obtained, it may be considered to make additional explorative analysis, based on a subset of ITT/PP populations.

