10.4. Pass/fail criteria

The purpose of this investigation is fulfilled if the performance of the products in the two arms is comparable in terms of wound area, while the mean total cost for Biatain® Silicone is significantly lower than for Standard of Care.

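### Total cost takes no account of time observed, so a subject who withdraws unhealed contributes a truncated count as a four-week cost, and the plan has no rule to complete or exclude it

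*Combined protocol and SAP*

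**What the plan says.** Section 10.1 gives the cost formula: "total cost, will be calculated as the number of products used during the investigational period multiplied by the unit price of the product". The arm means are then compared under a normality assumption: "It will be tested on a 2-sided 5% test level if the difference in mean between the two treatments is zero". Section 10.3 sets the same level for the whole trial: "A two-sided significance level of 5% will be applied".

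The ITT set in section 10.1 is "all randomized subjects with valid informed consent who have been exposed to at least one product". The per-protocol criteria concern eligibility, use of other dressings, infection and change of therapy, so they do not remove early withdrawals either. Section 10.2 expects such withdrawals: "To account for lost to follow-up/dropout rate of 20%, 100 subjects are required for this study". Section 5.1 adds: "Withdrawn subjects must also complete the Termination visit, regardless of the reason for withdrawal". No section describes counting dressings up to day 28 after that visit.

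Section 10.4 makes success depend on two conditions. One is that "the performance of the products in the two arms is comparable in terms of wound area", for which no margin or test is given. The other is that "the mean total cost for Biatain® Silicone is significantly lower than for Standard of Care".

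**The concern.** A four-week cost should be measured over four weeks. The formula counts products for as long as the subject is present. A subject who leaves unhealed after a week therefore carries about one week of dressings, although the wound still needs dressing elsewhere. A subject whose wound heals at one week carries much the same figure, and only there is the saving real. The formula cannot tell the two apart.

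This matters because the cost test is the only pass condition tied to statistical significance. Section 5.5 describes cost-effectiveness as a difference in total cost over the study period, which truncated counts do not measure. The trial is open-label (section 5.9), so withdrawal could differ between arms. Even when it does not, partial counts lower both means and add variance.

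**Working it through.** **Inputs from the documents.** Section 10.2: 40 completers per arm (80 in all) and 20% dropout. Check: 80 / (1 − 0.20) = 100, which reproduces the planned enrolment and, with equal arms, gives 50 per arm. The test is two-sided at 5%, so the nominal chance of a falsely lower test-arm cost is 2.5%. Section 4.7 expects 1–3 dressing changes a week. No standard deviation or power is given for cost.

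**Assumptions.** Four-week cost follows a gamma distribution with CV 0.3 or 0.5. It accrues in proportion to time. Withdrawal time is uniform over 28 days. The test is a two-sample t-test. The documents give none of the CV, the timing or any imbalance between arms.

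**Illustration.** At two changes a week, four weeks need 8 changes. A subject who leaves unhealed after one week is recorded with 2, or 25% of the four-week cost.

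**Bias in the means.** Let d be the dropout proportion and f the mean fraction of the period for which withdrawers are observed. The recorded share of the true mean is 1 − d(1 − f). With f = 0.5:

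- 20% in each arm: 1 − 0.20 × 0.5 = 0.90. Both means are 10% low and their ratio is unbiased.
- 25% (test) v 15% (standard of care): 0.875 / 0.925 − 1 = −5.4%.
- 30% v 10%: 0.85 / 0.95 − 1 = −10.5%.
- 15% v 25%: 0.925 / 0.875 − 1 = +5.7%.

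Timing matters. At 30% v 10%, f = 0.25 gives 0.775 / 0.925 − 1 = −16.2%, and f = 0.75 gives 0.925 / 0.975 − 1 = −5.1%.

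**False-saving rate.** Simulated with no true cost difference and 50 per arm:

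| Dropout, test v standard of care | Apparent difference | Falsely significantly lower, CV 0.3 / 0.5 |
|---|---|---|
| 20% v 20% | 0% | about 2.5% / 2.5% |
| 25% v 15% | −5.4% | 10% / 7% |
| 30% v 10% | −10.5% | 27% / 16% |
| 15% v 25% | +5.7% | 0.4% / 0.7% |

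**Power.** Assume a true 20% saving.

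- Everyone observed for 28 days: about 96% (CV 0.3) or 60% (CV 0.5).
- 20% dropout in each arm: about 77% or 47%.

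The loss comes from extra variance. The mean square of a uniform fraction is 1/3, so the CV of recorded cost is √[(1 + CV²)(0.8 + 0.2/3) − 0.9²] / 0.9. That is 0.41 in place of 0.3, and 0.58 in place of 0.5.

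**Effect of a common 28-day basis.** Scaling each subject's weekly cost to four weeks returned the false-saving rate to 2.3–2.7% in every dropout pattern tried (CV 0.2 to 0.5). This assumes that use before withdrawal represents use afterwards.

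**The case against.** The strongest reply is that the plan is silent and does not prescribe an error. Section 10.1 allows invalid data points to be omitted and sets a data review meeting before database lock, with the statistician blinded until then (section 5.9). A completer-only cost analysis could emerge from that. This stands in part: the documents do not say that partial counts will be analysed as complete costs. But they do not call a truncated count invalid either, and the formula applied to the ITT set produces one. Leaving the choice to the review meeting makes a pass/fail result depend on an unstated decision, and dropping withdrawers would bring its own selection.

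Three stronger readings are tempting, and the documents do not support them.

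- *The cost endpoint can never be missing.* Section 7.2.2 has changes between visits entered at the next scheduled visit, partly from a sheet the subject keeps. For a subject lost to follow-up, the last interval may be unknown.
- *The rule rewards the less acceptable dressing.* Section 5.1 keeps a subject whose wound needs another treatment in the investigation, and section 7.5 keeps such subjects in follow-up and in ITT. That narrows the most obvious route to arm-dependent loss. Voluntary withdrawal (section 6.3) remains possible, but nothing suggests more of it on the test product, and the reverse pattern works against that product.
- *The planned dropout itself inflates false positives.* At 20% in each arm it does not. A 30% v 10% split would be 15 v 5 of 50, which a disposition table would show.

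**Conclusion.** The point holds as a defect in the endpoint definition, limited to withdrawal and loss to follow-up. Applied as written to the ITT set, the formula treats a truncated count as a four-week cost, and neither the per-protocol set nor any other provision corrects it.

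Under equal 20% dropout the damage is to description and power: both means are about 10% low, and roughly 19 percentage points (CV 0.3) or 13 (CV 0.5) of power are lost for a true 20% saving. A biased pass/fail comparison needs unequal withdrawal, in number or timing, and its direction follows the imbalance. All sizes rest on the assumed CV, uniform timing, proportional cost and chosen imbalances. The mechanism itself rests only on sections 10.1 and 10.2.

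**What to change.** In section 10.1, define the endpoint as dressing cost over 28 days from baseline, with zero cost after the visit at which healing is first recorded. Healing is a yes/no item at visits, so the visit has to stand in for a date. For subjects who leave unhealed, treat the unobserved weeks as missing, including a last interval whose count was never returned. Complete them by a pre-specified method, for example multiple imputation from arm, wound type, baseline area and earlier weekly cost. Report the raw observed cost as a sensitivity analysis, with the number and timing of withdrawals by arm beside it.

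The counts and healing status are already collected at V2 to V5, so no new data are needed. The cost is some added wording, a little more analysis, and a missing-at-random assumption for the weeks after withdrawal. That assumption may fail if subjects leave because of the dressing, which is why the raw result and the withdrawal table should be shown with it.
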